3. STUDY METHODS AND PROCEDURES

All patients admitted to the TICU will have a documented GCS in the medical chart as a part of clinical care. [name] (LH), the study PI, and the Trauma Intensive Care Unit RN subinvestigators will screen the TICU census daily for new patients to identify those admitted with GCS ≤ 8 that meet study criteria. Eligible patients will be followed by the PI or the TICU RNs until the patient is assessed at GCS of 5 or above.

1. Patients with a GCS of 5 or above will be screened for eligibility. Those eligible will be invited to participate and consent will be obtained by study personnel.
2. Consenting subjects will be randomized to the intervention or control arm of the study

3. For patients randomized to the intervention arm, study personnel (PI or TICU RNs) will request a doctor's referral. A referral will be made to LH who will arrange for the patient to receive the intervention with the dog.
4. The control group will be receiving standard of care bedside interventions. During the control measurement period, the only person present will be the bedside nurse who records the measurements.
5. Study personnel will record the RLAS, GCS, Level of Commands, and Movement of Extremities within 24 hours of obtaining consent and order.

Intervention Group

1. When the patient is randomized to the treatment arm, the PI will refer the case to one of the AAC handler/dog teams approved for work on the study for the intervention. The AAC handler will respond within 3 days and will request data measurements be taken by the bedside RN. These measurements will include (see attachments for data collection sheet):
 - A. RLAS Score
 - B. GCS Score
 - C. Level of Command (LOCmd)-0, 1 or 2 or 3-step
 - D. Movement of Extremities
2. Following the recording of the above measurements, the AAC team will provide AAT to the patient.
3. Immediately following the intervention, the same scores will be measured by the same licensed healthcare professional.

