4. AAT and measurements of the same data will continue up to three times weekly after the initial measurements and will be listed on data collection sheets. If the patient is unavailable for AAT at the time of the scheduled intervention, the research team will document "unavailable," indicate the reason for unavailability. The patient will remain in the study and data collection will continue until the patient is discharged, reaches RLAS 7, or have been hospitalized ≥ 28 days. If the patient has been discharged from the study but remains in the hospital, he/she may continue to receive AAT.

Control Group

1. When the patient is randomized to the control arm, data measurements will be taken by the bedside RN. Variables to be collected include:
 - A. RLAS Score
 - B. GCS Score
 - C. Level of Command-0, 1 or 2 or 3-step (see same data collection sheet).
 - D. Movement of Extremities
2. The control group will be receiving standard of care bedside interventions. During the control measurement period, the only person present will be the bedside nurse who records the measurements. RLAS, GCS, and Level of Command and movement of extremities will be measured by the same licensed healthcare professional before and after each interaction with the healthcare professional.
3. The PI will be responsible for collecting measurements of the same data up to three times weekly after the initial measurements until they are discharged, reach RLAS 7, or have been hospitalized ≥ 28 days.

When the subject is moved to a different unit, study personnel will continue to be responsible for ensuring the study measurements, as measured by the bedside nurse, are recorded on the data collection form.

Methods for Tracking Recruitment and Retention. Study personnel will:

- Screen the trauma services database to determine the number of patients appropriate for the study.
- Keep detailed notes regarding the number of patients identified as potential participants by the study personnel to determine the percentage of eligible patients approached for inclusion into the study to determine the efficacy of our program to treat this population

- Keep detailed logs reflecting the number of patients approached to participate and the reasons for declining participation and for loss to follow up to determine the willingness of participants to consent to participate and remain in the study.

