4.2. Method of Data Analysis

Aim 1: To determine if the use of animal assisted therapy in the plan of treatment of patients with TBI results in higher scores on the Ranchos Los Amigos, Glasgow Coma Scale, an increased ability to follow commands, and an increased movement of extremities than those who do not receive AAT.

The difference in RLAS scores from pre-intervention to post the intervention will be the primary outcome for the analysis. The outcome, Δ RLAS, will be defined as RLAS during AAT/sham – RLAS pre-AAT/sham. Δ RLAS from each study visit (AAT or sham) will be averaged over each week of the study (weeks 1-4). To address the primary hypothesis, weekly Δ RLAS will be compared between the AAT group and controls using nonparametric Wilcoxon rank sum tests (Mann-Whitney U tests) in order to determine whether the AAT group has significantly higher Δ RLAS. This analysis will be stratified by weeks 1-4 to determine whether the difference in Δ RLAS between AAT and controls changes over time.

The difference in LOCmd scores and movement of extremities will be a secondary outcome of this study. Δ LOCmds and movement of extremities will be defined similarly to Δ RLAS, as the LOCmds and movement of extremities during AAT/sham – LOCmds and movement of extremities pre-AAT/sham, and the mean Δ LOCmds and movement of extremities will be calculated for each week of the intervention (1-4). Weekly

Δ LOCmd scores and movement of extremities will be compared between study groups (AAT vs. controls) using nonparametric Wilcoxon rank sum tests. This analysis will be stratified by weeks 1-4 to determine whether the difference in Δ LOCmd and movement of extremities between AAT and controls changes over time.

GCS scores are routinely collected every hour by the TICU nursing staff. Medical charts will be reviewed to record the GCS scores during the hour immediately before and immediately after the intervention (or sham) is implemented. Δ GCS will be defined as GCS after AAT/sham – GCS pre-AAT/sham. Weekly Δ GCS scores will be compared between study groups (AAT vs. controls) using nonparametric Wilcoxon rank sum tests. This analysis will be stratified by weeks 1-4 to determine whether the difference in Δ GCS between AAT and controls changes over time.

Aim 2: To determine if the use of animal assisted therapy in the plan of treatment of patients with TBI are discharged with a higher degree of cognitive function than those who did not receive AAT.

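### The enrolment RLAS, GCS, command and movement scores enter no planned comparison, and as listed they follow randomisation on a clock that is unclear for controls, so they are not yet a safe baseline.

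*Protocol*

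**What the plan says.** Protocol section 3 gives a numbered sequence. Step 1 is screening and consent. Step 2 is allocation: "Consenting subjects will be randomized to the intervention or control arm of the study". Step 3 applies to one arm: "For patients randomized to the intervention arm, study personnel (PI or TICU RNs) will request a doctor's referral". Step 4 describes the control condition. Step 5 is the enrolment assessment: "Study personnel will record the RLAS, GCS, Level of Commands, and Movement of Extremities within 24 hours of obtaining consent and order".

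The arm-specific instructions follow. In the intervention group, "The AAC handler will respond within 3 days and will request data measurements be taken by the bedside RN". In the control group, "When the patient is randomized to the control arm, data measurements will be taken by the bedside RN", with no time window attached.

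Section 4.2 defines the primary outcome as "RLAS during AAT/sham – RLAS pre-AAT/sham", averaged within each of weeks 1 to 4. It compares the arms "using nonparametric Wilcoxon rank sum tests (Mann-Whitney U tests) in order to determine whether the AAT group has significantly higher" change. Command level and movement of extremities are handled in the same way. The GCS outcome uses charted values: "Medical charts will be reviewed to record the GCS scores during the hour immediately before and immediately after the intervention (or sham) is implemented". No comparison names the step 5 scores, a covariate or a baseline stratum.

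Sections 3 and 3.4 end participation when a patient reaches RLAS 7. Section 1.2 hypothesises quicker and larger gains with AAT, and Aim 2 concerns cognitive function at discharge.

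**The concern.** There are two linked problems.

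**The score is collected but has no role.** Patients enter at any GCS from 5 upward and at whatever RLAS they have then reached. A patient who starts near RLAS 7 has less room to improve than one who starts low, and leaves the study sooner. Subtracting the pre-session score removes the level from each individual change. It does not remove the dependence of the change on that level. An enrolment score is the natural covariate for this and is already being recorded.

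**The score is not protected by randomisation.** A baseline earns its place in an adjusted analysis, or as the origin for a recovery hypothesis, by being measured before allocation, on the same terms in both arms. As listed, step 5 comes after allocation. Its clock refers to an order that controls are not described as receiving, and nothing says the scorer is unaware of the arm. RLAS, command level and movement are observer ratings, so knowledge of the arm could influence them.

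The stakes are comparability of the starting point for section 1.2 and Aim 2, and possibly some power.

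**Working it through.** **1. The plan's own figure.** Section 4.1 expects about 50 patients per group and states no alpha, power, effect size or SD, so no sample-size formula can reproduce it. The feasibility figures do not give it either. Section 2.4 reports about 100 eligible patients in 2011 and section 4.1 assumes 85% consent: 100 × 2 years × 0.85 = 170, and 100 × 0.85 = 85, against a stated total of 100. I take 50 per arm as given.

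**2. Sequence and clock, side by side.**

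| Item | AAT arm | Control arm |
|---|---|---|
| Randomisation | step 2 | step 2 |
| Doctor's referral | step 3 | none described |
| Enrolment scores | step 5, 24 h from consent and order | step 5, same wording, no order described |
| First session measurement | when the handler responds, within 3 days | no window stated |
| Enrolment scores used in 4.2 | no | no |

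If the order is the referral, the AAT clock can start later than consent and the control clock has no second trigger. If the order is something else, the protocol does not say what. Either way the window is not shown to be common to both arms.

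**3. Detectable difference without adjustment.** Assumed: two-sided alpha 0.05, 80% power, normal-theory comparison of two means in SD units as a stand-in for the rank analysis.

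d = (1.960 + 0.842) × √(2/50) = 2.802 × 0.2 = 0.560 SD.

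With the Wilcoxon efficiency under normality of 0.955: 0.560/√0.955 = 0.573 SD.

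**4. Adjusting for the enrolment score.** With correlation ρ between that score and the outcome, residual variance is multiplied by 1 − ρ². Power at d = 0.560 is Φ(2.802/√(1 − ρ²) − 1.960). The protocol gives no ρ, so this is a range.

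| ρ (assumed) | Variance factor | Detectable difference (SD) | Power at 0.560 SD |
|---|---|---|---|
| 0 | 1.00 | 0.560 | 80.0% |
| 0.1 | 0.99 | 0.558 | 80.4% |
| 0.2 | 0.96 | 0.549 | 81.6% |
| 0.3 | 0.91 | 0.535 | 83.6% |
| 0.5 | 0.75 | 0.485 | 89.9% |
| 0.7 | 0.51 | 0.400 | 97.5% |

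**5. What subtraction already achieves.** The outcome is a change score. Relative to a change score, adjusting for the pre-session value multiplies variance by (1 + r)/2, where r is the pre/post correlation. At r = 0.5, 0.8, 0.9 and 0.95 the factor is 0.75, 0.90, 0.95 and 0.975, and power is 89.9%, 84.0%, 82.0% and 81.0%. Over the short interval of a session r may well be high, in which case the extra gain is 1 to 2 percentage points. Pre-session scores after the first session are also poor covariates in principle, because they may already reflect AAT.

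**The case against.** The strongest reply has four parts.

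- **Starting values are not ignored.** A pre-session score is subtracted in every Δ, and for controls the step 5 score may be the same measurement as the first pre-session score. This is right. A reader might infer that baseline is unused altogether; only the separate enrolment score is unused.
- **Adjustment belongs in an SAP, and an unadjusted rank test is valid after randomisation.** The test is valid, and its type I error already allows for chance imbalance. But the protocol is not silent: it fixes the unadjusted test for each outcome. The order of scoring and allocation is trial procedure, and no SAP can repair it afterwards.
- **No loss of precision is demonstrated.** This also stands. The gain runs from almost nothing to large, depending on a correlation the protocol does not give. Nor does the late timing itself reduce precision; it affects comparability. While the score is collected as now written, leaving it out of the tests is the safer choice, so the procedural change must come first.
- **The timing is inferred.** It rests on list order, and step 4 describes continuing care, so the list may not be strictly chronological. Equating the order with the referral is plausible but not stated. That calls for clear wording; it does not show that the arms share a clock.

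A reader might also infer that the AAT enrolment score is taken up to 3 days late. The documents do not support that: the 3-day limit is the handler's response time and governs the pre-session measurement, not step 5.

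**Conclusion.** The point holds in a limited form. The step 5 scores have no role in section 4.2. Nothing places them before allocation, and their window is not defined on common terms for the two arms. The consequence is a comparability weakness: the score cannot safely serve as a covariate, or as the origin for the section 1.2 hypotheses and Aim 2, until its timing is fixed. It does not bias the planned Wilcoxon comparisons, since the score does not enter them.

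The benefit of adjusting once the timing is fixed is real in principle but of unknown size: 0.4 percentage points of power at ρ = 0.1, about 4 at 0.3 and about 10 at 0.5. This rests on 50 per arm, an assumed two-sided alpha of 0.05, a difference giving 80% unadjusted power, and a normal approximation to an ordinal outcome. The document does not establish that precision is being lost to any particular degree.

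**What to change.** 1. **Section 3.** Move step 5 ahead of step 2. State that RLAS, GCS, command level and movement are recorded for every patient within 24 hours of consent and before the allocation envelope is opened. Delete the reference to an order, and state what the scores are for.
2. **Section 4.2.** Add enrolment RLAS and GCS as covariates in each comparison, by rank ANCOVA or a proportional-odds model. Keep the plain Wilcoxon rank sum test as a sensitivity analysis.

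The second change depends on the first. The cost is protocol wording, slightly more analysis work, and an allocation that waits until the enrolment score is recorded. No new data are needed.

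### Only the AAT arm waits for a referral and a handler before its first score pair, so weekly ΔRLAS can compare the arms at different times after randomisation

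*Protocol*

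**What the plan says.** Protocol section 3 sets out common steps, then steps for each arm.

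- **AAT arm, referral.** After randomisation: "For patients randomized to the intervention arm, study personnel (PI or TICU RNs) will request a doctor's referral". No time limit is given.
- **AAT arm, handler.** The case then goes to a handler/dog team: "The AAC handler will respond within 3 days and will request data measurements be taken by the bedside RN". AAT follows those scores, and the scores are repeated afterwards.
- **Control arm.** "When the patient is randomized to the control arm, data measurements will be taken by the bedside RN". Scores are taken before and after each interaction with the healthcare professional. There is no referral, no handler and no slot matched to the AAT arm.
- **Common step 5.** "Study personnel will record the RLAS, GCS, Level of Commands, and Movement of Extremities within 24 hours of obtaining consent and order". This is not limited to one arm.
- **Frequency.** For the AAT arm: "AAT and measurements of the same data will continue up to three times weekly after the initial measurements". The control arm has the same ceiling.

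Section 4.2 defines the primary outcome, ΔRLAS, as the score during the session minus the score before it ("RLAS, will be defined as RLAS during AAT/sham"). The values are averaged within each of weeks 1-4 and compared between arms by week. The day from which weeks are counted is not given. Under section 3.4, participation ends at RLAS 7, at discharge or at 28 days of hospitalisation, among other reasons.

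**The concern.** A comparison by week needs the same time axis in both arms. So does the hypothesis in section 1.2 that AAT patients improve faster as well as further. Here two steps that take time stand between randomisation and the first usable AAT observation, and neither exists for controls.

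Two things are at stake. First, week 1 (or, depending on how weeks are counted, every week) may describe the arms at different times after randomisation. Second, a patient who reaches RLAS 7, is discharged, dies or is not referred before the first dog visit drops out of the primary analysis if allocated to AAT, but may stay in it if allocated to control. That is loss after randomisation in one arm only. Section 3 itself foresees that mortality may require more subjects.

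**Working it through.** The protocol gives no figure of its own to reproduce here. The check sets the two sequences side by side and does day arithmetic.

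**1. Path to the first score pair**

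| Step | AAT | Control |
|---|---|---|
| Doctor's referral after randomisation | required, no time limit | none |
| Handler response | up to 3 days | none |
| First pair | at the first dog visit | no stated wait or deadline |
| Single score within 24 hours of consent and order | yes | yes |

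The 24-hour score does not remove the difference. It is a single recording, ΔRLAS needs two scores around a session, and no AAT session can happen before the handler comes. The only order or referral described is in the AAT arm, so even the 24-hour clock may start later there. The text does not say whether this score is a separate baseline or the first pre-session score. If it is the latter, it conflicts with a response allowed to take 3 days.

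**2. Largest gap in the first pair (AAT minus control)**

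Gap = referral time + handler response − control start. The handler maximum of 3 days is from the protocol; the other two values are assumptions.

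- Referral immediate, control on day 0: 0 + 3 − 0 = 3 days.
- Referral immediate, control at 24 hours: 0 + 3 − 1 = 2 days.
- Referral takes 1 day, control on day 0: 1 + 3 − 0 = 4 days.

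If the handler response were uniform over 0-3 days (assumption), its mean would be 1.5 days. The mean gap would then run from 0 + 1.5 − 1 = 0.5 to 1 + 1.5 − 0 = 2.5 days.

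**3. Effect on the weeks, with the handler step at its maximum**

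- *Weeks counted from randomisation:* AAT week 1 loses 3/7 = 42.9% of its days. At an even rate and the ceiling of three sessions a week, 3 × 4/7 = 1.7 sessions fit instead of 3.
- *Weeks counted from the first session:* every AAT week lies up to 3 days later after randomisation than the same control week. The 28-day limit runs on hospital days and does not move with the wait, so up to 3/28 = 10.7% of a four-week span is not recovered at the end.

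Neither origin aligns the arms.

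**4. Loss before the first pair**

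The protocol gives no exit rate. For illustration, with about 50 patients per arm, suppose 2%, 5% or 10% leave during the wait:

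- 50 × 0.02 = 1
- 50 × 0.05 = 2.5
- 50 × 0.10 = 5

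These AAT patients have no ΔRLAS. Comparable controls can have one if their first pair is taken early.

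**The case against.** Five points can be made on the other side.

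- **Not all AAT scoring waits.** Correct. Common step 5 foresees a score within 24 hours in both arms. Only the pair waits, but the primary outcome is built on pairs.
- **The control start is not fixed either.** A reader might infer that controls are scored at the moment of randomisation. The wording that opens the control steps has a parallel in the AAT steps and may simply introduce the arm. The documents permit an earlier control start; they do not prescribe it.
- **ΔRLAS is measured within a session.** A reader might infer that the later AAT start puts days of natural recovery into the AAT result. It does not, because each patient is compared with a score taken just before the same session. Stage of recovery can act only indirectly, through the RLAS level at the start (room to improve, exit at RLAS 7) and through who is left to be measured. Having fewer sessions makes a weekly mean noisier but does not by itself bias it.
- **The figures are ceilings and assumptions.** Correct. Three days and three sessions a week are both maxima, and the exit rates are not from the protocol. Refused referrals may be few, since allergy, isolation, dislike of dogs and religious or cultural reasons are already exclusions.
- **The week origin and patients without data belong in an SAP.** Partly so. An SAP can define week 1. It cannot create score pairs that were never taken, and the order of randomisation, referral and first visit is fixed in the protocol.

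**Conclusion.** The point holds in limited form. Only the AAT arm has a referral step without a time limit and a handler wait of up to 3 days before its first score pair, and nothing aligns the control sessions with that wait. The 24-hour rule supplies at most a single score and is not reconciled with the 3-day response. The weekly ΔRLAS comparison can therefore set the arms side by side at different times after randomisation, and early losses can remove AAT patients but not similar controls.

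The handler step accounts for at most 3/7 of week 1, plus any referral delay. The documents do not support reading 43% as the expected loss, or treating the mismatch as certain. They also do not support a claim that the trial is biased in a known direction: they give no recovery, exit or referral rates, and the route to bias is indirect. The change is still worth making, because it is cheap and the missing pairs cannot be recovered at analysis.

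**What to change.** Reorder the steps in section 3 and use one start rule for both arms:

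1. Obtain the doctor's referral and identify the first available AAC visit slot for every consenting patient before the envelope is opened. Patients who are not referred are then not randomised.
2. Take the first score pair in that slot in both arms: around AAT in one, around standard bedside care in the other.
3. Count weeks 1-4 from the date of that slot in both arms.
4. Keep all randomised patients in the count, and report by arm the number without any score pair.
5. State in common step 5 that the 24-hour score is a separate baseline, not the first pre-session score.

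The content of AAT and the session ceiling do not change. The cost is that referrals and slots are also arranged for patients who become controls, and the first control pair may be taken a few days later. Exits between randomisation and the slot remain possible, but the wait is then the same in both arms.

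### An unblinded bedside nurse scores both halves of the primary RLAS change, and no planned analysis compares the arms on recovery over time; a supportive comparison of pre-session scores would do so cheaply

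*Protocol*

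**What the plan says.** Protocol section 3 fixes who rates and when. In the intervention arm the handler "will request data measurements be taken by the bedside RN", the dog team then works with the patient, and straight afterwards "the same scores will be measured by the same licensed healthcare professional". For controls, "During the control measurement period, the only person present will be the bedside nurse who records the measurements"; that nurse scores before and after ordinary care. No blinded or independent rater is described. Study personnel also record one baseline set, including RLAS and Level of Commands (LOCmd), within 24 hours of consent and order.

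Section 4.2 fixes the outcome and the test. The primary outcome "will be defined as RLAS during AAT/sham – RLAS pre-AAT/sham". It is averaged within each week and compared between arms by Wilcoxon rank sum test for each of weeks 1 to 4. LOCmd and movement of extremities are handled in the same way. For the Glasgow Coma Scale (GCS), "GCS scores are routinely collected every hour by the TICU nursing staff", and the chart values for the hour before and the hour after the session are compared between arms. The text under Aim 2, which concerns cognitive function at discharge, repeats the within-session comparisons.

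Hypothesis 1 (section 1.2) is about a quicker and greater rise in RLAS, GCS and command-following, that is, a course over time.

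**The concern.** One person who knows the allocation gives both scores in the difference. In the AAT arm the second score follows a dog visit; in the control arm it follows routine care by the nurse alone. Section 4.2 uses the word sham, but section 3 describes no sham visit. Any tendency to score up after a dog visit therefore falls on one arm and on one half of the difference, and randomisation does not remove it.

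The planned analyses offer no second view. Pre-session RLAS is used only as the value subtracted, and chart GCS only in the hours next to the session. A positive result could reflect rater expectation, a brief arousal response or better recovery, and nothing in section 4.2 would help to tell lasting recovery from the other two.

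**Working it through.** **Inputs from the Protocol.** About 50 patients per arm (section 2.4); up to three sessions a week (section 3: "AAT and measurements of the same data will continue up to three times weekly after the initial measurements"); weekly mean change compared by Wilcoxon test (section 4.2). The protocol states no alpha, effect size, SD, noise rate or bias rate, so there is no planned power figure to reproduce.

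**Assumptions.** Two-sided 5% test; no true effect; sessions independent within a patient. A rating moves up one level with probability u and down one level with probability v in either arm. In the AAT arm the upward probability becomes u + 0.10, meaning one session in ten is scored one level too high. The AAT arm's mean is then 0.10 level higher per session.

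**Cross-check by formula.** The variance of one session's change is (up + down) − (up − down)². For u = 5%, v = 2%:
- control: 0.07 − 0.03² = 0.0691
- AAT: 0.17 − 0.13² = 0.1531
- average 0.1111, SD 0.333; mean of three sessions: 0.333/√3 = 0.192
- standardised shift d = 0.10/0.192 = 0.52
- rejection ≈ Φ(d√(50/2) − 1.96) = Φ(5 × 0.52 − 1.96) = Φ(0.64) ≈ 74%

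The other settings follow in the same way. The average variance is 0.245 for 10% noise each way and 0.445 for 20% each way.

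| Sessions per week | Noise up / down | d | Formula | Simulated Wilcoxon |
|---|---|---|---|---|
| 3 | 5% / 2% | 0.52 | 74% | 72% |
| 3 | 10% / 10% | 0.35 | 42% | 41% |
| 3 | 20% / 20% | 0.26 | 25% | 27% |
| 1 | 5% / 2% | 0.30 | 32% | 32% |
| 1 | 10% / 10% | 0.20 | 17% | 17% |

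The noisiest corner (one session, 20% each way) has d = 0.10/0.667 = 0.15 and gives Φ(0.75 − 1.96) ≈ 11%. With no over-scoring the simulated test rejects in about 4% to 6% of trials. The inflation is real in every setting, but its size depends on noise and session frequency.

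**What the scores already collected could show.** Take the change from baseline to the last pre-session RLAS, 50 per arm, with an assumed SD of 1.0 to 1.5 levels:
- over-scoring in 20% of AAT sessions, confined to the post-session or during-session score: the comparison rejects in 4% to 6% of trials, the nominal level. At the same 20%, with three sessions a week and noise of 5% to 20% each way, the weekly within-session test rejects in 67% to 97%
- the same over-scoring carried fully into the pre-session score: 9% to 14%
- a true gain of 0.5 level: power 35% to 65%
- a true gain of 1 level: power 89% to 99.9%

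**The case against.** A dog visit cannot be hidden from bedside staff. Using one rater for both scores limits between-rater variation, and the protocol is open about the arrangement. All of that stands. Supportive analyses are often left to a statistical analysis plan. Here, however, the protocol itself fixes the rater, the endpoint and the test, and its own hypothesis is left without a matching comparison.

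A reader might infer several stronger things that the document does not support:
- That rater bias will produce a positive trial. The protocol gives no bias or noise rates, so only *can* is justified. The 72% comes from the most sensitive setting; three sessions a week is the maximum, and over-scoring is placed only in the AAT arm although the control nurse also re-scores after her own care.
- That the rater is in the room throughout. The text does not say so. It does show that the nurse, asked by the handler to score before and immediately after, knows that a visit took place.
- That chart GCS goes unused as a test of treatment. It is compared between arms, but only for the hours around the session.
- That pre-session scores are blinded and would expose rater bias. The same bedside nurse makes them at the handler's request, and the listed order of steps places even the baseline after randomisation. A null result could mean rater bias or a real effect that fades.
- That no efficacy claim should be made unless both analyses agree. With 35% to 65% power for a half-level gain, such a rule would often fail a real effect, and would fail a purely acute one by design.

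**Conclusion.** The point holds as a design and interpretation weakness. The rater knows the arm, controls have no matching visit, and every efficacy analysis in section 4.2 is a within-session difference, so no analysis addresses the recovery course in Hypothesis 1 or shows persistence beyond the session. If one AAT session in ten is scored one level high and there is no true effect, a weekly test is positive in about 17% to 72% of trials over the five tabulated settings, and about 11% in the noisiest corner, against a nominal 5%. These figures rest wholly on assumed noise and bias rates, independent sessions and 50 patients contributing per arm. They show what is possible and do not predict the result.

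**What to change.** In section 4.2:
- Pre-state a supportive between-arm comparison of change from the baseline RLAS and LOCmd to the pre-session scores in each week. The first pre-session score precedes any AAT, so later weeks carry the information.
- Collection stops at RLAS 7. Carry those patients' scores forward or rank them as best, so that the fastest recoverers are not dropped.
- Describe the within-session change as an unblinded acute response that does not by itself support a claim of improved recovery.
- Reconcile the timing of the second score: during the session in section 4.2, immediately afterwards in section 3.

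Do not make agreement between the analyses a condition for any claim. A chart GCS from the next nursing shift is optional: it is a different scale, hourly recording is stated only for the trauma ICU, and that nurse may also know the arm.

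The cost is a little more analysis work, with no new assessor. The remaining limits are that the pre-session rater may know the arm, and that a null result cannot separate rater bias from a real short-lived effect. The addition is a supportive check of persistence, not proof against bias.
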